## 5.2.2.1. Reasons for Permanent Discontinuation of Study Drug

Part A consists of only 1 dose.

Part B: Study drug dosing in individual subjects will be permanently stopped for any of the following reasons:

- The infant experiences acute systemic injection reactions with AEs including, but not limited to, anaphylaxis, laryngeal/pharyngeal edema, severe bronchospasm, seizure, or severe hypotension
- The infant experiences a Grade 3 or greater drug-related AE

- The infant has an RSV-positive RT-PCR result at the study central laboratory or a CLIA (or equivalent) certified laboratory after receipt of the first dose of study drug, but prior to the second dose of study drug.
- The parent(s) or legal guardian(s) of a subject withdraws consent
- A decision is made by the sponsor to stop treating an individual subject with study drug
- A decision is made by the sponsor to stop the study (Section 3.2)

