# 7.2. Recording and Reporting Adverse Events

#### **7.2.1.** Adverse Events

The investigator (designee) will record all AEs that occur from the time the ICF is signed until the end of study. Refer to the study manual for the procedures to be followed.

Information on follow-up for AEs is provided in Section 7.2.7. Laboratory test results or vital signs are to be recorded as AEs as outlined in Section 7.2.6.

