## 7.2.6. Abnormal Laboratory or Vital Sign Results

The criteria for determining whether an abnormal objective test finding will be reported as an AE include any of the following:

- The test result is associated with accompanying symptoms,
- The test result requires additional diagnostic testing or medical/surgical intervention,
- The test result leads discontinuation from the study treatment, discontinuation from the study, significant additional concomitant drug treatment, or other therapy,
- Grade 3 or higher laboratory test result abnormalities

The investigator will contact the medical monitor in the event the investigator feels that an abnormal test finding should be reported as an AE, although it does not meet any of the above criteria.

Repeating an abnormal test, in the absence of any of the above conditions will not constitute an AE. Any abnormal test result that is determined to be an error will not require reporting as an AE.

Evaluation of severity of laboratory abnormalities will be assessed according to the scale outlined in Section 7.3.1.

Regeneron Pharmaceuticals, Inc.

Page 81 of 137

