Only medically attended respiratory illness occurring during the 150-day efficacy assessment period will be considered for the primary endpoint. If categorization of a MARI event as an endpoint is unclear, source documentation will be provided to a blinded adjudication committee for categorization prior to database lock.

If an infant has a medically attended respiratory event but did not have an RT-PCR test conducted in the central laboratory within 14 days after onset of the episode of RSV illness, results from a RSV RT-PCR assay conducted in the local lab will be used to determine RSV infection if the RSV RT-PCR assay is reviewed by jurisdictional health authority and released for commercial distribution, or conducted in a laboratory that is currently certified for human diagnostic testing. To that end, protocol has specified the following conditions for acceptable local lab RSV RT-PCR assays:

- Assay is a FDA-cleared RSV RT-PCR assay or
- Assay is an RSV RT-PCR assay that is not FDA-cleared but is conducted in a laboratory that is currently CLIA (or equivalent) certified.

The algorithm to programmatically derive an observed primary endpoint event is depicted in [Figure 2](#).

Figure 2 Flow diagram to depict the programmatic derivation of an observed primary endpoint event

Answers to questions (1) through (7) in the flow diagram are collected from the following electronic case report form (eCRF) pages and other source data:

- Questions (1) and (3): eCRF page of “History of Medically-Attended Acute Respiratory Illness (MARI) Questionnaire”.
- Question (2): eCRF page of “Hospitalization for Respiratory Illness Questionnaire”.
- Question (4): eCRF page of “Lower Respiratory Infection (LRI) Questionnaire”.
- Questions (5): eCRF page of “Central Laboratory” for nose swab collection and eCRF page of “History of Medically-Attended Acute Respiratory Illness (MARI) Questionnaire” for AE start date.
- Question (6): Central lab RSV RT-PCR test results from Viracor.
- Questions (7) and (8): eCRF page of “Unscheduled RSV RT-PCR (Local Lab)”

On the eCRFs, the MARI questionnaire, the LRI questionnaire, and the central (or local) lab RSV PCR test(s) are designated by the investigator to a corresponding medically-attended acute respiratory adverse event (AE). Therefore, the corresponding AE serves as the key variable to programmatically merge information from the MARI and LRI pages with RSV PCR test(s) for each episode of illness.

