4.7.1. Adverse Events and Serious Adverse Events

The definitions for AEs and serious adverse events (SAEs) are described in Sections 7.1.1 and 7.1.2 of the study protocol, respectively. Additional information on determining whether abnormal laboratory or vital sign results should be considered as AEs is included in Section 7.2.6 of the study protocol. AEs and SAEs will be collected from the time of informed consent signature and then at each visit until the end of the study.

The severity of AEs is graded using 1 of 2 severity scales. The severity scale used is determined by the type of AE experienced by the subject; more detail is provided in Section 7.3.1 of the protocol.

Adverse Event Observation Period

- Pre-treatment AEs are AEs that developed or worsened or became serious during the pre-treatment period.
- Treatment-emergent AEs (TEAEs) are defined as AEs that are not present at baseline or represent the exacerbation of a preexisting condition during the SAFETY TREATMENT period (TEAE period). Therefore, referencing the protocol, TEAEs will be defined programmatically as any AE record with a start date/time on or after the first study drug administration (greater than or equal to study day 1), inclusive to the end of the TEAE period.
- Post-treatment AEs are AEs that developed or worsened or became serious during the POST-TREATMENT period.

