5.8.1. Adverse Events

The verbatim text, the PT, and the primary SOC will be listed in subject listings. Summaries that include frequencies and proportions of subjects reporting AEs will include the PTs and the SOCs as appropriate.

The focus of adverse event reporting in the clinical study report will be on TEAEs. Pre-treatment and post-treatment AEs will be provided separately.

If an AE date/time of onset (occurrence, worsening, or becoming serious) is incomplete, an imputation algorithm will be used to classify the AE as pre-treatment, treatment-emergent, or post-treatment. The algorithm for imputing date/time of onset will be conservative and will classify an AE as treatment-emergent unless there is definitive information to determine pre-treatment status. For details on handling missing data and partial dates, see Section 6.3.

Summaries of all TEAEs in each treatment group will include:

- Overview of TEAEs, summarizing number and percentage of subjects with any
 - TEAEs.
 - Serious TEAEs.
 - TEAEs leading to death.
 - TEAEs leading to permanent treatment discontinuation.
 - TEAEs with severity of 3/4/5/Severe/Life-Threatening/Fatal (if multiple occurrences of an event for a subject, then worst severity is counted).
 - TEAEs that occurred within 2 days after either the first dose or the second dose (ie, post dose TEAE start date - dosing date \leq 2).
- All TEAEs by SOC and PT.
- All TEAEs by SOC, PT, and severity.
- All TEAEs by SOC, PT, and relationship (related, not related) to study drug.
- All TEAEs by SOC, PT, and relationship (related, not related) to injection procedure.
- TEAEs reported by \geq 5% of subjects in any treatment group by PT ordered by decreasing subject frequency in the combined REGN2222 group.
- TEAEs reported by \geq 1% of subjects in any treatment group by PT ordered by decreasing subject frequency in the combined REGN2222 group.
- Study drug-related TEAEs by SOC and PT.
- Study drug-related TEAEs by SOC, PT, and severity.
- Injection procedure-related TEAEs by SOC and PT.
- Injection procedure-related TEAEs by SOC, PT, and severity.

- Serious adverse events: All, study drug-related, and injection procedure-related TEAEs by SOC and PT.
- Death: All, study drug-related, and injection procedure-related TEAEs by SOC and PT. TEAEs leading to death are TEAEs that led to death regardless of timing of death in relation to study drug injection (ie, death occurring in the TEAE period or during the post-treatment period)

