- Discontinuation of study drug: All, study drug-related, and injection procedure-related TEAEs by SOC and PT.
- TEAEs with severity of 3/4/5/Severe/Life-Threatening/Fatal: All, study drug-related, and injection procedure-related TEAEs by SOC and PT.
- Non-serious study drug-related or injection procedure-related TEAEs by SOC and PT.
- TEAEs according to time of occurrence in relation to dosing:
 - TEAEs that occurred after the first dose and before the second dose: All, study drug-related, and injection procedure-related TEAEs by SOC and PT. For subjects who did not receive the second dose, only TEAEs that occurred up to Day 57 (Day 1 being the day when the first dose was administered) will be included.
 - TEAEs that occurred after the second dose in subjects who received the second dose: All, study drug-related, and injection procedure-related TEAEs by SOC and PT.
 - Serious TEAEs that occurred after the first dose and before the second dose: All, study drug-related, and injection procedure-related TEAEs by SOC and PT. For subjects who did not receive the second dose, only serious TEAEs that occurred up to Day 57 (Day 1 being the day when the first dose was administered) will be included.
 - Serious TEAEs that occurred after the second dose in subjects who received the second dose: All, study drug-related, and injection procedure-related TEAEs by SOC and PT.
 - TEAEs with severity of 3/4/5/Severe/Life-Threatening/Fatal that occurred after the first dose and before the second dose: All, study drug-related, and injection procedure-related TEAEs by SOC and PT. For subjects who did not receive the second dose, only relevant TEAEs that occurred up to Day 57 (Day 1 being the day when the first dose was administered) will be included.
 - TEAEs with severity of 3/4/5/Severe/Life-Threatening/Fatal that occurred after the second dose in subjects who received the second dose: All, study drug-related, and injection procedure-related TEAEs by SOC and PT.
 - TEAEs that occurred within 2 days after either the first dose or the second dose (ie, post dose TEAE start date - dosing date \leq 2): All, study drug-related, and injection procedure-related TEAEs by SOC and PT.

- TEAEs that occurred within 2 days after the first dose: All, study drug-related, and injection procedure-related TEAEs by SOC and PT.

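### SAP 5.8.1 does not separate study-drug stops forced by the RSV-positive RT-PCR rule, so its AE-discontinuation summaries may mix efficacy failures with intolerance

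*SAP*

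**What the plan says.** **The stop.** Protocol 5.2.2.1 introduces its Part B list with "Study drug dosing in individual subjects will be permanently stopped for any of the following reasons". One entry is "The infant has an RSV-positive RT-PCR result at the study central laboratory or a CLIA (or equivalent) certified laboratory", limited to results after the first dose and before the second. It stands beside acute systemic injection reactions and drug-related AEs of Grade 3 or above.

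**The adverse event.** Protocol 7.2.1 says the investigator "will record all AEs that occur from the time the ICF is signed until the end of study", with no exemption for endpoint events. SAP 4.6.1 says the respiratory illness questionnaires and the RSV PCR tests "are designated by the investigator to a corresponding medically-attended acute respiratory adverse event (AE". SAP 4.7.1 programs a TEAE as "any AE record with a start date/time on or after the first study drug administration (greater than or equal to study day 1", up to the end of the TEAE period. Protocol 7.2.6 gives as one criterion for reporting an abnormal finding as an AE: "The test result leads discontinuation from the study treatment, discontinuation from the study, significant additional concomitant drug treatment, or other therapy".

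**The display.** SAP 5.8.1 has an overview row, "TEAEs leading to permanent treatment discontinuation", and a table, "Discontinuation of study drug: All, study drug-related, and injection procedure-related TEAEs by SOC and PT". Protocol 9.5.3.3 asks for the same summary. None of these separates stops made under the RSV rule. SAP 5.8 makes all safety summaries descriptive and presents the combined REGN2222 group in order to look for safety signals. SAP 3.2 assigns infants to safety columns by the number of REGN2222 doses they actually received.

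**The concern.** A summary of AEs that led to stopping is normally read as a measure of tolerability. Here one of the mandatory reasons for stopping is the infection the product is meant to prevent. If such stops are attributed to the respiratory AE, part of the row measures efficacy with the sign reversed: the better REGN2222 works, the worse placebo looks. A real excess of intolerance stops on REGN2222 could then be offset, or a placebo excess could be taken for better tolerability. The overview row is the most exposed, because it gives one count per column with no preferred terms.

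**Working it through.** **Inputs from the documents.** Primary event rates are 10% on placebo and 4% on REGN2222 over 150 days, with 505 per arm and about 90 events expected (Protocol 9.2). Enrolment was cut to about 1200, so 400 per arm (Protocol 9.2, SAP 2.2). Dose 2 is on Day 57, which leaves about 56 days in which the rule can act.

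**Check on the plan's own figures.** A continuity-corrected chi-square test of 10% against 4% at two-sided 0.025 and 90% power needs 480 per arm. Then 480/0.95 = 505.3, or 506 rounded up, against 505 stated. Events: 505 × (0.10 + 0.04 + 0.04) = 90.9, against about 90. The rates are therefore the ones the plan uses. The documents give no expected discontinuation rate.

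**Assumption.** The share *s* of the 150-day risk that falls before dose 2 is not in the documents. Uniform risk gives s = 56/150 = 0.37; the range used is 0.25 to 0.60. Every primary event in that window is taken to lead to a stop that is attributed to the AE.

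**RSV-rule stops = 150-day rate × s**

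| s | Placebo (of 400) | REGN2222 combined (of 800) | Difference |
|---|---|---|---|
| 0.25 | 2.5% (10) | 1.0% (8) | 1.5 points |
| 0.37 | 3.7% (15) | 1.5% (12) | 2.2 points |
| 0.60 | 6.0% (24) | 2.4% (19) | 3.6 points |

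A constant hazard in place of uniform risk gives 1 − 0.90^(56/150) = 3.9% and 1 − 0.96^(56/150) = 1.5%, much the same.

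**What this could hide.** Suppose, for illustration only, that true non-RSV stop rates were 0.5% on placebo and 2.0% on REGN2222. The displayed rate is p + b − pb, where p is the RSV-rule rate and b the non-RSV rate.

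- s = 0.37: placebo 0.0373 + 0.005 − 0.0002 = 4.2%; REGN2222 0.0149 + 0.020 − 0.0003 = 3.5%. The direction is reversed.
- s = 0.25: placebo 0.025 + 0.005 − 0.0001 = 3.0%; REGN2222 0.010 + 0.020 − 0.0002 = 3.0%. The excess disappears.

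**Individual dose columns.** At s = 0.37 each randomized REGN2222 arm has 400 × 0.0149 = 6.0 RSV-rule stops. In the 2-dose arm those infants have received one REGN2222 dose, so SAP 3.2 places them in the 1-dose column. That column then holds 11.9 of 406 (2.9%), and the 2-dose column 0 of 394. Only the combined column shows 1.5%.

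**What could move these figures.** The protocol trigger is any qualifying positive RT-PCR, so upper-tract RSV illness would add stops. In the other direction, a positive from a non-PCR assay, or from a laboratory without the required certification, does not stop dosing (Protocol 6.2.2.4), and a result may not be known by Visit 4. If REGN2222 has no effect, RSV-rule stops are equal across the randomized arms and there is no placebo excess.

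**The case against.** The strongest objection is that the link from stop to AE is inferred. Protocol 5.2.2.1 lists the RT-PCR result as a reason in its own right, apart from the AE-based reasons. Protocol 7.2.6 governs whether a finding is reported as an AE, not whether a stop is attributed to it. If sites record the stop as a protocol reason only, the tables will hold few such cases. This stands, so the conclusion has to be conditional. A reader might infer that the tables necessarily count every RSV illness as an AE discontinuation. The documents do not support that: attribution is not shown, and only a qualifying RT-PCR result between the two doses triggers the stop.

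The second objection is that the plan already shows what is needed. SAP 5.8.1 asks for drug-related and procedure-related versions, where RSV illness should be rare, as well as a by-PT display and a subject listing. Protocol 9.4.2 adds a listing of reasons for stopping treatment. There is no formal safety testing. This also stands in part: there is no type I error issue, and a careful reader of the detailed tables would see much of the cause. It does not rescue the overview row. Nor need a respiratory preferred term name RSV, since RSV status comes from the merged PCR result.

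A reader might also take 1.5% as the figure for each REGN2222 column. SAP 3.2 rules that out, as shown above.

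**Conclusion.** The point holds in conditional form. Where sites attribute the mandated stop to the respiratory AE, the SAP 5.8.1 overview row and the All version of the discontinuation table will mix efficacy failures with intolerance stops, and the placebo column will be the higher if REGN2222 works. Under the design rates and an assumed 25% to 60% of risk before Day 57, RSV-rule stops amount to 2.5% to 6.0% on placebo and 1.0% to 2.4% in the REGN2222 combined column. An intolerance excess on REGN2222 of roughly 1.5 to 3.6 percentage points could be offset. The individual dose columns are distorted further by the as-treated grouping. This is a weakness in how a descriptive table can be read, partly mitigated by the other displays. It should be corrected because the correction is simple and the descriptive tables are the whole of the safety evaluation.

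**What to change.** In SAP 5.8.1, keep the total and add two sub-rows to the overview and to the SOC/PT table:

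- (a) stops whose recorded reason is the RSV-positive RT-PCR rule;
- (b) all other TEAEs that led to a permanent stop.

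Name (b), REGN2222 combined against placebo, as the tolerability comparison. Footnote that the as-treated dose columns are not comparable for stops before dose 2, since the split does not cure that.

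Define the flag from the recorded reason for stopping together with the qualifying RT-PCR result. The RT-PCR date and a missing dose 2 are not enough: an RT-PCR-positive infant may also have missed dose 2 through the fever and antipyretic rule, withdrawn consent or a sponsor decision (Protocol 5.2.2.1 and 6.3.1.1). Sub-row (b) can still contain AE-linked stops under the fever rule, which the footnote should say.

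The stop trigger also differs between documents. Protocol 5.2.2.1 ties it to a qualifying positive RT-PCR, whereas SAP 2.3 and SAP Appendix 11.2 tie it to reaching the primary endpoint. These passages must be reconciled before the flag is defined.

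The cost is SAP wording and one derived variable, with no change to trial conduct. If the eCRF does not capture the reason for stopping, a blinded review before database lock would be needed. At the design rates that concerns about 400 × 0.18 × s RSV-rule stops in total, or 18 to 43 infants for s from 0.25 to 0.60.
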